13.5 Appendix 5: Tuberculosis Risk Questionnaires

13.5.1 Tuberculosis Risk Questionnaire for Screening Visit

The following questions are to be asked to every subject for evaluation of signs and symptoms of tuberculosis (TB). Responses to each question must be documented on this source document.

Question	Response
1) Does the subject have a currently active TB disease or a history of active TB disease?	 Yes  No
2) Has the subject been in close contact (i.e., sharing the same household or other enclosed environment, such as a social gathering place, workplace, or facility, for extended periods during the day) with an individual with active TB within the past 1.5 years?	 Yes  No
3) Is the subject a TB hospital, forensic medical examination, or morgue employee?	 Yes  No
4) Does the subject work or has the subject stayed in long-stay institutions (e.g., homes for the elderly or disabled, prisons, etc.)?	 Yes  No
5) Does the subject reside in, did the subject ever reside in, or is the subject frequently travelling to a TB endemic region (as defined in Table 7)? (only applicable for subjects not living in an endemic region)	 Yes  No
6) Is the subject in frequent contact with underprivileged populations (homeless people or other people needing social assistance)?	 Yes  No
7) Does the subject have a new cough lasting more than 14 days or a change in a chronic cough?	 Yes  No
8) Does the subject have night sweats?	 Yes  No
9) Does the subject have a persistent fever?	 Yes  No
10) Does the subject have unintentional weight loss (more than 10% of body weight) in the past 3 months?	 Yes  No
11) Does the subject appear malnourished?	 Yes  No
12) Has the subject had an abnormal chest X-ray since the last evaluation?	 Yes  No

Physician's signature: _____

13.5.2 Tuberculosis Risk Questionnaire for Post-Screening Visits

The following questions are to be asked to every subject for evaluation of signs and symptoms of tuberculosis (TB). Responses to each question must be documented on this source document.

Question	Response
1) Does the subject have a new diagnosis of active TB disease?	 Yes  No
2) Has the subject been in close contact (i.e., sharing the same household or other enclosed environment, such as a social gathering place, workplace, or facility, for extended periods during the day) with an individual with active TB since the last scheduled visit?	 Yes  No
3) Has the subject become an employee of a TB hospital, forensic medical examiner, or morgue since the last scheduled visit?	 Yes  No
4) Has the subject started work or has the subject stayed in long-stay institutions (e.g., homes for the elderly or disabled, prisons, etc.) since the last scheduled visit?	 Yes  No
5) Does the subject reside in or is the subject frequently travelling to a TB endemic region (as defined in Table 7)? (only applicable for subjects not living in an endemic region)	 Yes  No
6) Has the subject been in frequent contact with underprivileged populations (homeless people or other people needing social assistance) since the last scheduled visit?	 Yes  No
7) Does the subject have a new cough lasting more than 14 days or a change in a chronic cough?	 Yes  No
8) Does the subject have night sweats?	 Yes  No
9) Does the subject have a persistent fever?	 Yes  No
10) Does the subject have unintentional weight loss (more than 10% of body weight) in the past 3 months?	 Yes  No
11) Does the subject appear malnourished?	 Yes  No
12) Has the subject had an abnormal chest X-ray since the last evaluation?	 Yes  No

Physician's signature: _____

Table 7 List of Endemic TB Countries (Incidence >50/100,000)

Country	Incidence ^a	Country	Incidence ^a	Country	Incidence ^a
Afghanistan	189 (167–212)	Greenland	197 (173–223)	Nigeria	322 (189–488)
Algeria	78 (64–94)	Guatemala	57 (51–64)	Northern Mariana Islands	61 (53–69)
Angola	370 (240–529)	Guinea	177 (156–199)	Pakistan	270 (201–350)
Azerbaijan	77 (68–86)	Guinea-Bissau	369 (261–495)	Papua New Guinea	417 (304–547)
Bangladesh	227 (200–256)	Guyana	103 (91–116)	Peru	120 (98–145)
Belarus	58 (50–67)	Haiti	200 (177–225)	Philippines	288 (254–324)
Benin	61 (50–74)	India	167 (156–179)	Romania	81 (71–91)
Bhutan	164 (148–181)	Indonesia	399 (274–546)	Russia	84 (76–93)
Bolivia	120 (106–135)	Ivory Coast	165 (150–179)	Rwanda	63 (54–72)
Botswana	385 (361–410)	Kazakhstan	99 (64–141)	Sao Tome and Principe	97 (85–109)
Brunei	62 (54–70)	Kenya	246 (240–252)	Senegal	138 (122–154)
Burkina Faso	54 (48–59)	Kiribati	497 (406–597)	Sierra Leone	310 (235–394)
Burundi	126 (116–136)	Kyrgyzstan	142 (126–160)	Solomon Islands	86 (71–102)
Cabo Verde	138 (122–156)	Laos	189 (141–244)	Somalia	274 (242–308)
Cambodia	390 (353–428)	Lesotho	852 (612–1130)	South Africa	834 (737–936)
Cameroon	220 (195–247)	Liberia	308 (273–346)	South Korea	86 (81–91)
Central African Republic	375 (333–420)	Lithuania	62 (57–68)	South Sudan	146 (121–173)
Chad	159 (141–179)	Madagascar	235 (207–264)	Sri Lanka	65 (57–73)
China	68 (63–73)	Malawi	227 (122–365)	Sudan	94 (52–148)
China, Hong Kong	74 (65–84)	Malaysia	103 (83–124)	Swaziland	733 (533–963)
China, Macao	82 (72–93)	Mali	58 (56–59)	Tanzania	327 (155–561)
Congo	381 (335–430)	Marshall Islands	335 (274–402)	Tajikistan	91 (80–103)

Country	Incidence ^a	Country	Incidence ^a	Country	Incidence ^a
Democratic Republic of Congo	325 (295–356)	Mauritania	111 (79–148)	Thailand	171 (90–276)
Djibouti	619 (547–696)	Micronesia	195 (87–347)	Timor-Leste	498 (411–594)
Dominican Republic	60 (53–68)	Moldova	153 (135–172)	Togo	58 (47–70)
Ecuador	54 (39–71)	Mongolia	170 (149–193)	Turkmenistan	64 (52–78)
Equatorial Guinea	162 (142–184)	Morocco	106 (97–115)	Tuvalu	190 (154–228)
Eritrea	78 (57–103)	Mozambique	551 (435–680)	Uganda	161 (141–183)
Ethiopia	207 (168–250)	Myanmar	369 (334–406)	Ukraine	94 (83–106)
Fiji	67 (55–81)	Namibia	561 (492–635)	Uzbekistan	82 (61–107)
Gabon	444 (393–497)	Nauru	73 (64–83)	Vanuatu	63 (52–74)
Gambia	174 (145–206)	Nepal	158 (139–178)	Vietnam	140 (116–167)
Georgia	106 (99–114)	Nicaragua	58 (53–63)	Yemen	48 (42–54)
Ghana	165 (80–281)	Niger	98 (87–110)	Zambia	406 (279–557)
				Zimbabwe	278 (193–379)

Abbreviations: HIV = human immunodeficiency virus; TB = tuberculosis; WHO = World Health Organization.

a. Rate per 100,000 population

Note: ranges represent uncertainty intervals.

Note: The 30 WHO TB high burden countries are as follows: Angola, Bangladesh, Brazil, Cambodia, China, Congo, Central African Republic, Democratic Republic of Congo, Ethiopia, India, Indonesia, Kenya, Lesotho, Liberia, Mozambique, Myanmar, Namibia, Nigeria, Pakistan, Papua New Guinea, Philippines, Russian Federation, Sierra Leone, South Africa, South Korea, Thailand, the United Republic of Tanzania, Viet Nam, Zambia, and Zimbabwe.

Source: WHO Global Tuberculosis Report 2015.

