5.4 Study Procedures

Every effort should be made to ensure that the protocol-required tests and procedures are completed as described. However, it is anticipated that from time to time there may be circumstances outside of the control of the Investigator that may make it unfeasible to perform the test. In these cases, the Investigator will take all steps necessary to ensure the safety and well-being of the subject.

The timing for all study visits during the double-blind Treatment Period (Visit 3 [Week 1] through Visit 15 [Week 24]) is relative to baseline (Visit 2 [Week 0]). The timing for all study visits during the Safety Follow-Up Period (Visits SFU-1, SFU-2, and SFU-3) is relative to the last dose of study treatment (+4, +8, and +22 weeks, respectively).

As much as possible, subjects should be seen for all scheduled visits on the designated day. If a subject is unable to attend a scheduled visit on the designated day, the subject should be seen as closely as possible to the originally scheduled visit day.

The following visit windows are allowed (see Table 1 and Table 2), although their use should be avoided if possible:

- Visit 1 (Screening) and Visit 2 (baseline): ± 0 days
- Visit 3 (Week 1): ± 2 days
 - Subjects in the sample-rich PK subpopulation must adhere to a ± 1 -day visit window for Visit 3 (Week 1)
- Visits 4 through 15/EoT (Weeks 2 through 24): ± 3 days
 - Subjects in the sample-rich PK subpopulation must adhere to a ± 1 -day visit window for Visit 4 (Week 2), Visit 5 (Week 4), Visit 14 (Week 22), and Visit 15/EoT (Week 24)
 - Additional restrictions for the sample-rich PK subpopulation are as follows:
 - Visit 13 (Week 20) should be scheduled to fall within 14 ± 2 days after Visit 12 (Week 18) and 28 ± 3 days after Visit 11 (Week 16).
 - Visit 14 (Week 22) should be scheduled to fall within 14 ± 1 days relative to study treatment administration at Visit 13 (Week 20)
 - Visit 15/EoT (Week 24) should be scheduled to fall within 28 ± 1 days relative to study treatment administration at Visit 13 (Week 20).
- Visits SFU-1, SFU-2, and SFU-3: ± 7 days

A detailed discussion of the visit schedule and visit windows for the sample-rich PK subpopulation can be found in Section 7.2.

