- Record weight.

- Perform complete physical examination (see Section 7.6.7.1).
- Record vital signs.
- Perform chest X-ray.
 - Chest X-ray need not be conducted if performed and evaluated within 8 weeks prior to the EoT Visit, and if the films or images are available and included in the subject's source documents.
- Perform 12-lead ECG.
- Collect samples for INR, aPTT, and fibrinogen.
- Measure ESR.
- Collect sample to measure CRP level.
- Collect samples for lipid panel and CV risk panel.
 - Subjects must attend study sites after fasting (water and concomitant medications are permitted) for at least 9 hours for the purpose of conducting the lipid panel assessment.
- Collect sample for serum biomarkers related to targeted pathway.
- Collect samples for chemistry panel, hematology, ANAs, and dsDNA antibodies assessments.
 - Subjects must attend study sites after fasting (water and concomitant medications are permitted) for at least 9 hours for the purpose of conducting the chemistry panel.
- Collect samples for measurement of anti-CCP and RF.
- Collect PK sample (see Table 5).
- Collect sample for analysis of ADAs.
- Perform urine pregnancy test for females of childbearing potential only.
- Collect sample for urinalysis.

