5.4.3 Safety Follow-up: Visits SFU-1, SFU-2, and SFU-3

5.4.3.1 Visit SFU-1 (Week 26 or 4 Weeks after the Last Dose of the Study Treatment)

The following assessments will be conducted 4 weeks after the last dose of the study treatment:

- Record AEs.
- Record details of contraceptive history/status.
- Record concomitant medications and concomitant non-drug therapies.
- Record weight.
- Perform partial physical examination (see Section 7.6.7.1).
- Record vital signs.
- Collect sample to measure CRP level.
- Perform urine pregnancy test for females of childbearing potential only.

5.4.3.2 Visit SFU-2 (Week 30 or 8 Weeks after the Last Dose of the Study Treatment)

The following assessments will be conducted 8 weeks after the last dose of the study treatment:

- Record AEs.
- Record details of contraceptive history/status.
- Record concomitant medications and concomitant non-drug therapies.
- Administer TB risk questionnaire.
- Record weight.
- Perform partial physical examination (see Section 7.6.7.1).
- Record vital signs.
- Collect sample to measure CRP level.
- Collect samples for chemistry panel and hematology assessments.
 - Subjects must attend study sites after fasting (water and concomitant medications are permitted) for at least 9 hours for the purpose of conducting the chemistry panel.

- Collect PK sample (see Table 5).
- Collect sample for analysis of ADAs.
- Perform urine pregnancy test for females of childbearing potential only.

5.4.3.3 Visit SFU-3 (Week 44 or 22 Weeks after the Last Dose of the Study Treatment)

The following assessments will be conducted 22 weeks after the last dose of the study treatment:

- Record AEs.
- Record details of contraceptive history/status.
- Record concomitant medications and concomitant non-drug therapies.
- Record weight.
- Perform complete physical examination (see Section 7.6.7.1).
- Record vital signs.
- Perform 12-lead ECG.
- Collect samples for INR, aPTT, and fibrinogen.
- Collect samples for lipid panel and CV risk panel.
 - Subjects must attend study sites after fasting (water and concomitant medications are permitted) for at least 9 hours for the purpose of conducting the lipid panel assessment.
- Collect samples for chemistry panel, hematology, ANAs, and dsDNA antibodies assessments.
 - Subjects must attend study sites after fasting (water and concomitant medications are permitted) for at least 9 hours for the purpose of conducting the chemistry panel.
- Collect sample for analysis of ADAs.

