 - Hepatitis C (HCV Ab) Lipid panel: Total cholesterol, HDL, LDL, triglycerides, lipoprotein (a), apolipoproteins (apolipoprotein B [ApoB], apolipoprotein A1 [ApoA1], and ApoB:ApoA1 ratio), and adiponectin
- Cardiovascular risk panel: N-terminal pro-hormone of brain natriuretic peptide (NT-proBNP), brain natriuretic peptide (BNP), and homocysteine

- HbA_{1c} (at Screening only)
- Anti-CCP and RF (at Screening and EoT Visit only)
- ANA and dsDNA antibodies
- IGRA (at Screening and Visit 14 only)
 - IGRA is to be performed at Screening (Visit 1) and the result is to be known prior to randomization to determine the subject's eligibility for the study (see exclusion criterion No. 19 in Section 5.3.2). If indeterminate, the IGRA can be repeated once during the Screening Period.
 - IGRA is to be performed at Visit 14 (Week 22) for all subjects who had a negative IGRA result at Screening. If indeterminate, the IGRA can be repeated once.
 - Subjects who had a positive IGRA result at Screening and were subsequently enrolled in the study following treatment for LTBI will not undergo the scheduled IGRA at Visit 14 (Week 22).
 - Details of the assessment are provided in the Laboratory Manual.
- ADAs: The actual sample collection date and exact time will be entered on the Immunogenicity Blood Collection eCRF page. Sampling problems will be noted in the Comments section of the eCRF. All blood samples will be taken by either direct venipuncture or an indwelling cannula inserted in a forearm vein. A Laboratory Manual will be provided to the Investigators with detailed information on sample collection, handling, and shipment. Tubes and preprinted labels will be provided by the central laboratory to the study sites.
- Pharmacogenetics and Biomarkers: The actual sample collection date and exact time will be entered on the corresponding Blood Collection eCRF pages. Sampling problems will be noted in the Comments section of the eCRF. All blood samples will be taken by either direct venipuncture or an indwelling cannula inserted in a forearm vein. A Laboratory Manual will be provided to the Investigators with detailed information on sample collection, handling and shipment. Tubes and preprinted labels will be provided by the central laboratory to the study sites.

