7.6.9 Tuberculosis Risk Questionnaires

The questionnaires “Tuberculosis Risk Questionnaire for Screening Visit” and “Tuberculosis Risk Questionnaire for Post-Screening Visits” (see Appendix 5 [Section 13.5]) should be used as source documents. The questionnaire “Tuberculosis Risk Questionnaire for Screening Visit” will be completed at Visit 1 (Screening), and the questionnaire “Tuberculosis Risk Questionnaire for Post-Screening Visits” will be completed at Visits 7, 10, 15, and SFU-2 as noted in Table 1 or Table 2 (as applicable).

At the Screening Visit, if question No. 1 (Does the subject have currently active TB disease or a history of active TB disease) or question No. 2 (Has the subject been in close contact [i.e., sharing the same household or other enclosed environment, such as a social gathering place, workplace, or facility, for extended periods during the day] with an individual with active TB within the past 1.5 years) of the questionnaire “Tuberculosis Risk Questionnaire for Screening Visit” is answered “Yes” the subject is not allowed to enter the study (see exclusion criterion No. 19, Section 5.3.2). A “Yes” response to any of the other questions within the questionnaire at Screening should trigger further careful assessment to determine the subject’s risk of TB disease.

At all post-Screening visits, a “Yes” response on the “Tuberculosis Risk Questionnaire for Post-Screening Visits” should be treated as follows:

- Question 1: If a subject answers “Yes” study treatment should be discontinued if active TB is confirmed (see Section 6.11).
- Questions 2 through 6: if a subject answers “Yes” to any question, they should be assessed (TB risk questionnaire and physical examination) 12 weeks from the time of exposure to determine if the subject developed TB. The Investigator should consult with a certified TB specialist or pulmonologist, if needed.
- Questions 7 through 12: if a subject answers “Yes” to any question, this should trigger a careful assessment to determine if the subject developed TB (see Section 7.6.10).

This risk questionnaires are not to be used to exclude TB disease or confirm diagnosis.

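### The post-Screening TB form asks about exposure only since the previous scheduled visit, so read literally it leaves 20 of the 30 weeks from baseline to the last form unasked

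*Combined protocol and SAP*

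**What the plan says.** Section 7.6.9 has the post-Screening form "completed at Visits 7, 10, 15, and SFU-2 as noted in Table 1", that is, at Weeks 8, 14, 24 and 30. Tables 1 and 2 and the visit lists in Section 5.4 agree. For example, 5.4.3.2 (SFU-2) lists "Administer TB risk questionnaire", while SFU-1 and SFU-3 have no such item.

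The form is in Section 13.5.2. Question 2 asks about close contact "with an individual with active TB since the last scheduled visit". Question 3 reads "Has the subject become an employee of a TB hospital, forensic medical examiner, or morgue since the last scheduled visit". Questions 4 (long-stay institutions) and 6 (underprivileged populations) use the same look-back. Question 5 (endemic regions) has no look-back, but applies only to subjects who do not live in an endemic region. Question 12 (chest X-ray) uses a different anchor, the last evaluation.

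For a positive answer to any of questions 2 to 6, Section 7.6.9 says "they should be assessed (TB risk questionnaire and physical examination) 12 weeks from the time of exposure", with specialist consultation if needed. Such an answer does not by itself stop study treatment.

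**The concern.** During treatment subjects attend at least every other week, but the TB form is used at only four post-Screening visits. A look-back to the previous scheduled visit therefore does not reach back to the previous form. Exposure that begins and ends between the windows is never asked about, and the interval from the Screening form to baseline is also missed.

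The wording of two items widens the gap. Question 3 asks whether the subject has become an employee, and one limb of question 4 asks whether the subject has started work. Someone who began at a TB hospital in Week 3 and still works there could truthfully answer no to question 3 on every form. Continuing contact is captured by questions 2 and 6 and by the other limb of question 4.

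What is at stake is the 12-week check, which starts only if the exposure is known. The protocol treats contact as important: contact within 1.5 years before Screening is exclusionary (criterion 19b). Two of the four planned countries, Russia (84 per 100,000) and Belarus (58), are on its own endemic list in Table 7. For subjects living there question 5 does not apply, so every applicable exposure question has this look-back.

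**Working it through.** The plan gives no figure on this point, so there is none to reproduce. The check is interval arithmetic on the visit weeks in Table 1, for a subject who stays on treatment and enters Safety Follow-Up.

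**Coverage.** Literal coverage of a form = form week − week of the scheduled visit just before it.

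| Form | Preceding scheduled visit | Weeks covered | Unasked weeks before it |
|---|---|---|---|
| Visit 7, Week 8 | Visit 6, Week 6 | 2 | 0–6 (6) |
| Visit 10, Week 14 | Visit 9, Week 12 | 2 | 8–12 (4) |
| Visit 15, Week 24 | Visit 14, Week 22 | 2 | 14–22 (8) |
| SFU-2, Week 30 | SFU-1, Week 26 | 4 | 24–26 (2) |
| Total | | 10 of 30 | 20 of 30 (67%) |

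**Variants.**
- Adding up to 4 Screening weeks: 24 of 34 (71%).
- Rolling over to the extension at Week 24: 6 + 4 + 8 = 18 of 24 (75%).
- SFU-2 at 12 weeks after the last dose (Week 34), as Section 5.2.2 has it: the Week 34 form covers 8 weeks, so 14 of 34 are covered and 20 are still unasked.

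**Visit windows** (±3 days up to Visit 15; SFU-1 and SFU-2 at last dose + 28 and + 56 days, ±7).
- Longest coverage: 20 + 20 + 20 + 42 = 102 days. The last form is then on day 154 − 3 + 56 + 7 = 214, and 112/214 = 52% is unasked.
- Shortest coverage: 8 + 8 + 8 + 14 = 38 days. The last form is then on day 154 + 3 + 56 − 7 = 206, and 168/206 = 82% is unasked.

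**Can the routine forms stand in for the 12-week check?** Reassessment date = exposure week + 12, compared with forms at Weeks 8, 14, 24 and 30. How close a form must fall is my assumption.

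| Tolerance | Unasked weeks with a form near the 12-week date |
|---|---|
| ±1 week | 5 of 20 |
| ±2 weeks | 10 of 20 (Weeks 0–4, 10–12, 16–20) |
| ±3 weeks | 15 of 20 |

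At ±2 weeks the other 10 (Weeks 4–6, 8–10, 14–16, 20–22 and 24–26) have no nearby form. For exposure in Weeks 18–22 and 24–26 (6 weeks) the reassessment date falls after the last form. For rollover subjects, 6 of 18 unasked weeks have a nearby form at ±2 weeks; any forms in the extension are not in these documents.

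**After rewording.** With the look-back anchored to the previous form, and baseline used for the first, coverage is 8 + 6 + 10 + 6 = 30 of 30 weeks. Anchoring the first form to Screening adds the Screening interval.

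**The case against.** The strongest reply is that the gap exists only on a literal reading. The questions are put to the subject by staff and a physician signs the form. A sensible clinician may well take the phrase to mean since this was last asked, and the gap is then zero. That stands as a limit on the practical effect. It does not remove the defect: no section defines the phrase that way, and question 12 on the same form uses a different anchor.

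A second reply is that other safeguards exist: the Week 22 IGRA, the End of Treatment chest X-ray, symptom questions, adverse event questioning, the instruction to report symptoms of infection at once, and the rule in 7.6.10 to stop dosing on evidence of TB. Physical examinations are done at every visit; on a ±2-week rule one falls near the 12-week date for 16 of the 20 unasked weeks (all but 20–22 and 24–26). These do limit harm, but none asks about contact, and the questionnaire half of the 12-week step is still missed. Other limits apply:
- The Week 22 IGRA is not done in subjects enrolled after a positive Screening IGRA and LTBI treatment.
- For exposure in Weeks 10–12, 14–22 and 24–26 (12 of the 20), the Week 22 test does not come 12 or more weeks afterwards.
- Section 7.6.3.1 itself warns that signs of inflammation may be muted on such agents.

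Third, calendar share is not risk. Household or workplace contact often persists into a window, and national incidence does not show how many short contacts would be lost. That is correct, and the percentages should not be read as missed exposures or missed cases.

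**Conclusion.** The concern holds. As written, four exposure questions leave 20 of 30 weeks (67%; 52% to 82% across the allowed visit windows) unasked for subjects who complete treatment and enter Safety Follow-Up, and 18 of 24 (75%) for those rolling over. This rests on a literal reading and on scheduled attendance. It does not apply to subjects who stop early, whose End of Treatment and follow-up visits are timed from their last dose. The statement that half of the unasked weeks have no form near the 12-week date depends on the ±2-week tolerance; across ±1 to ±3 weeks the share without one runs from 75% to 25%. The consequence is a weakened TB exposure check in a trial that plans sites in two endemic countries. Efficacy endpoints, alpha and power are untouched. The change should be made, because the defect is clear in the text and the remedy is small.

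**What to change.** In questions 2, 3, 4 and 6 of Section 13.5.2, replace the look-back with: *since the last TB questionnaire (for the first post-Screening form, since Screening)*. This closes the gap through Week 30 and also resolves the onset wording in questions 3 and 4, because every start date then falls inside some form's interval.

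It does not detect Screening-period contact before the first dose (first asked about at Week 8), and it does not cover Weeks 30–44. The actions that follow a positive answer are unchanged.

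The cost is four reworded questions, with no added visit, test or staff. Because the form is a protocol appendix, the change should travel with a protocol amendment and its ethics committee handling. Recall lengthens from 2–4 weeks to 6–10 weeks, and up to 12 for the first form. A few more positive answers will need the follow-up that 7.6.9 already describes.
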